In either entry method, patients interested in quitting smoking will be eligible for either the Cessation Study or the Long-term Quitting Study, and they will be randomized to one of these two studies. The amount and level of randomization of those interested in quitting to these two projects will be adjusted in order to meet study recruitment goals. This adjustment may include assigning subjects to only one of the two quitting studies if necessary to achieve the necessary balance and overall recruitment required for the primary analyses. Smokers expressing an interest in cutting down on their smoking will be eligible for the Motivation Study. Patients who pass the phone screen will be invited to attend a study session at their referring clinic (where all treatment visits will occur), where they will learn more about the study, have eligibility confirmed, and provide written informed consent. Records collected in this research will allow us to determine the overall reach of the intervention within the clinic (e.g. percentages and demographic characteristics of patients who complete each recruitment step) and will allow us to complete a full CONSORT diagram.

Communication that includes essential PHI between each participating health system clinic and UW-CTRI research staff takes place for two purposes. First, following verbal consent, the clinic communicates information about their patients interested in hearing about the study to UW-CTRI. This information will include patient name, contact information (phone, address) available and responsible clinic provider and MR number (all necessary to contact patients and to fully match referred patients and complete the data analysis at the end of the study). (Note: Second, UW-CTRI must communicate back specific information about those patients consented. This information communicated after written consent is obtained and includes the name of the enrolled patient and over-the-counter (OTC) medication (dosage and duration) provided by the

“Breaking Addiction to Tobacco for Health (BREATHE) Study”

PI: [name], MPH, MBA; UW-CTRI Center Grant: 1P01CA180945-01.

study to the patient. As described below, these communications will take place without any UW-CTRI staff having access to any additional patient medical record information and without health system staff having access to any additional research information.

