**Study Procedures, including Visits and Phone Contacts**

All participants will attend an initial in-person baseline visit at their primary care clinic where they will provide written informed consent, receive information on assigned intervention components, complete assessments, provide a breath sample for carbon monoxide (CO) assessment, and receive initial treatment based on their treatment condition. After the initial visit, study participation will include phone calls and/or additional in-person visits to provide interventions and collect data.

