### **The Intervention Components**

All 3 studies will use as their primary interventions nicotine replacement therapy for treating smokers and one or more specific types of counseling. They will also employ the same research staff (referred to as health counselors) with each health counselor trained to provide all types of counseling. The research will use specific quality/fidelity assurance strategies that include: intensive case manager training in counseling and ethical conduct, mock sessions, review of audiotapes, and meetings to discuss safety, confidentiality, and treatment fidelity. Health counselors will meet every other week for clinical supervision with a clinical psychologist investigator to review the study protocol and address treatment issues. A common database provides guidance on the counseling content, medication and assessments to be provided at each contact. Such procedures have produced excellent treatment delivery fidelity in our recent work. The distinct intervention components are detailed below.

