Specific eligibility requirements for all 3 clinical studies within the intervention clinics are: 1) 18 years of age or older; 2) report smoking at least 5 cigarettes per day for the previous 6 months; 4) able to read and write English; 5) have reliable phone access and agree to respond to Interactive Voice Response (IVR) phone prompts 8) free of medical contraindications to NRT; and 9), if participant is a woman of childbearing potential, using an approved method of birth control during treatment. Participants who are eliminated due to screening failure, or elect not to participate in this research medication program, will be given a list of alternative smoking cessation programs, including an opportunity to receive usual care from the clinic and a referral to the Wisconsin Tobacco Quit Line ([name]). For the Motivation Study, participants also have to be not currently attempting to quit smoking or intending to quit smoking (defined as no plans to quit in the next month); and planning to remain in the intervention catchment area for at least 12 months. For the Cessation Study, participants also have to be motivated to quit smoking and planning to remain in the intervention catchment area for at least 12 months. For the Long-term Quitting Study, participants also have to be motivated to quit smoking and planning to remain in the intervention catchment area for at least 2 years and 2 months.

A minimum of 2112 participants will be recruited to participate in this research: 512 in the Motivation Study, 600 in the Cessation Study and 1000 in the Long-term Quitting Study. However, to get a proper balance of participants across the three studies, we may recruit as many as 2600. No special vulnerable populations will be intentionally recruited (pregnant women will be specifically screened out due to medication safety concerns and no persons under the age of 18 will be allowed to participate because the medications we are using have not been approved by the FDA for individuals less than 18 years old). See the Inclusion/ Exclusion section for protocol regarding participants previously eligible who become incarcerated or pregnant.

Eligible participants will be randomized at the point of screen passing the phone screen (stratified by gender). Those who do not enroll will be unrandomized and the treatment condition assigned to them will be reassigned to a new preparticipant.

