risks associated with nicotine toxicity, nicotine withdrawal, and the pharmacotherapies. The health counselor will then provide each study candidate with an IRB-approved informed consent document corresponding with the study which they have chosen. Study candidates will read the informed consent document and be given an opportunity to ask any questions regarding study participation. A research staff member will read the consent form to the study candidate if needed or desired. The consent form will include necessary HIPAA language. Participants will be required to sign the consent form. Case managers will provide participants with a copy of the consent form.

*Protection Against Risk.* Risks related to medications are minimized through close monitoring. The leader for each study (Project Leaders), working in consultation with the Program Project’s physician ([name]), will be responsible for routine monitoring of unanticipated health events. This risk protection includes procedures for contacting the emergency physician or psychologist and monitoring of all events through scheduled biweekly meetings with study staff and review of written documentation. Unanticipated health event assessment, recording, reporting and investigation will be accomplished through staff training, structured/standardized assessments of untoward occurrences/events, and regular monitoring by study physicians and other study investigators. The Project Leaders and the Program Project Co-Principal Investigators have ultimate responsibility for ensuring that unanticipated health events are detected and reported in a timely manner. Health events that raise concerns (e.g., allergic reaction, symptoms suggestive of nicotine toxicity, significant change in mood, suicidal ideation) will be immediately reported to the study physician who will determine an appropriate course of action.

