**Data Collection for Patients Visiting the Clinic During the Recruitment Period**

- Medical Assistants (MAs) complete EMR-recorded tobacco use screening. The following visit record information will be analyzed from the EMR during specified recruitment time periods in each clinic:
  - Number of unique adult patients (18 years and older) with visits during the recruitment period
  - Number of visits by those unique patients
  - Clinic
  - Smoking status: not asked, never, current, former
  - Study referral: yes/no
- UW-CTRI research staff send the following data to EMR data staff via secure server for all those sent for consenting to study participation and contact with their health clinic (by clinic subsequent to the close of the recruitment period):
  - Name
  - Date of visit where referral took place
  - MR #
  - Clinic
- EMR data staff sends the following group data to research staff via secure server for 7 different groups for each clinic participating in the study: (1) those not asked about smoking at all visits (2) those indicating they are a never smoker at any visit; (3) those indicating former smoker at any visit, (4) those indicating smoking at any visit but not invited to study by attending medical staff (5) those indicating smoking at any visit not interested in being referred at any visit, (6) those referred but not enrolled in the study and (7) those enrolled in the study.
  - Gender distribution
  - Ethnicity distribution (African American, white, other)
  - Age distribution (5 year increments, over 80 as a single group)
  - Types of insurance (commercial, Medicaid, self-pay, etc.)
  - Diagnosis (ICD-9, grouped into categories)
  - Visit type and level
  - Number of clinic visits during the study period (1, 2, 3, 4 or more)
  - Visit at which study invitation was accepted (groups 5 and 6 only)

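### Motivation and Cessation Studies: treatment condition is assigned before consent, with no stated concealment from consent-taking staff and no stated count of non-enrollers by assigned condition

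*Combined protocol and SAP*

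**What the plan says.** The order of events has to be pieced together from several sections.

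- **Assignment.** Protection of Human Subjects, Risks to the Subjects: "Eligible participants will be randomized at the point of screen passing the phone screen (stratified by gender").
- **Non-enrollers.** Same place: "Those who do not enroll will be unrandomized and the treatment condition assigned to them will be reassigned to a new preparticipant".
- **Eligibility and consent.** Recruitment & Study Entry puts these after the phone screen, at a clinic session where people "learn more about the study, have eligibility confirmed, and provide written informed consent". Study Procedures lists, for the baseline visit, that participants "provide written informed consent, receive information on assigned intervention components". The condition therefore exists before consent, and the participant is told of it afterwards.
- **Who takes consent.** Recruitment and Informed Consent: "The health counselor will then provide each study candidate with an IRB-approved informed consent document corresponding with the study which they have chosen". The Intervention Components makes the same health counselors the treatment providers and adds: "A common database provides guidance on the counseling content, medication and assessments to be provided at each contact". It does not say when the database first shows the condition.
- **Reporting.** Recruitment & Study Entry promises a full CONSORT diagram. Appendix 1 asks for aggregate data on groups that include ("6) those referred but not enrolled in the study and (7) those enrolled in the study"), per clinic and not by assigned condition. The Appendix 2 chart is not in the text available here.

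The passage on phone-screen randomisation names no study. It refers to a treatment condition, which in the Motivation Study means a combination of the four factors and in the Cessation Study means AOCT or M-UC. In the Long-term Quitting Study everyone receives the same initial treatment, and the tested randomisations come at relapse and at the new quit attempt, after consent. The allocation of people who want to quit, where "they will be randomized to one of these two studies", is a separate, study-level step.

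**The concern.** Randomisation protects the comparison only if the decision to enrol cannot depend on the assigned condition. Here assignment comes first and enrolment second, treatment is open-label, and nothing stated keeps the assignment from the person conducting the consent visit. Participants appear to learn their condition only after signing, so the open route is staff knowledge: how fully the study is explained, how hard a visit is pursued, how a borderline eligibility point is judged.

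The conditions give staff reason to expect different uptake or adherence. In the Cessation Study, M-UC has one 10-minute session and one quitline call. AOCT has three 20-minute visits and eight 15-minute calls, 3×20 + 8×15 = 180 minutes, plus 7 or 11 automated calls. In the Motivation Study the range runs from no counseling to 10 + 10 + 4 = 24 component sessions of 10–15 minutes (240–360 minutes), with or without a year of mini-lozenges.

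If enrolment did differ by condition, analysing everyone enrolled as assigned would not repair it, because the people lost are outside the data set. The usual warning sign, unequal arms, is removed because vacated conditions are re-issued until the arms are full.

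**Working it through.** **The plan's own figures.** Pooled two-proportion test, two-sided α = .05, normal approximation. Cessation Study, 20% vs 30% at 300 per arm: power .809 (plan: .80). Motivation Study quit attempts, 60% vs 72% at 256 per level: power .819 (plan: .81). Both reproduce; this point disputes neither.

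**How many people are removed.** The documents give no rate of non-enrolment after the phone screen, so let f be an assumed rate. Ever assigned = enrolled / (1 − f), rounded up.

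| f | Motivation, 512 enrolled | Cessation, 600 enrolled |
|---|---|---|
| .10 | 569 (57 removed) | 667 (67) |
| .20 | 640 (128) | 750 (150) |
| .30 | 732 (220) | 858 (258) |
| .40 | 854 (342) | 1,000 (400) |

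**What arm-dependent enrolment would do.** Assume a fraction x of would-be enrollees is lost from one arm only, and that those lost would have been abstinent with probability r. If the true rate is .20, the rate among those who enrol is p = (.20 − x·r) / (1 − x). For example, x = .15 and r = .05 give p = (.20 − .0075)/.85 = .2265. At 300 enrolled per arm:

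| x | r | p | Lost from AOCT, true 20% vs 20%: type I error | Lost from M-UC, true 20% vs 30%: difference in points; power |
|---|---|---|---|---|
| .05 | .10 | .2053 | .053 | 9.5; .763 |
| .05 | .05 | .2079 | .057 | 9.2; .737 |
| .10 | .10 | .2111 | .063 | 8.9; .705 |
| .10 | .05 | .2167 | .079 | 8.3; .646 |
| .15 | .10 | .2176 | .083 | 8.2; .635 |
| .15 | .05 | .2265 | .124 | 7.4; .534 |

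The false difference under the null is p − .20, that is 0.5 to 2.6 points. The direction depends on who is lost. If the 10% lost from M-UC would have quit at 30–40%, the result is a false AOCT advantage of 1.1–2.2 points with a rejection rate of .064–.107. If those lost would have quit at the arm's own rate (r = .20), there is no bias.

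**What re-issue hides.** Without re-issue, 600 enrollees would split as 600(1 − x)/(2 − x) in the arm with the loss: 292 vs 308 at x = .05 and 276 vs 324 at x = .15. With re-issue the split is 300/300 whatever x is.

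**What a log by assigned condition would show.** Take background non-enrolment of 20% and 300 enrolled per arm. M-UC needs 300/.80 = 375 assigned, so 75 non-enrollers. AOCT needs 300/(.80(1 − x)):

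| x | AOCT assigned | AOCT enrolment | AOCT non-enrollers | Power to detect the difference from 80% |
|---|---|---|---|---|
| .05 | 395 | 76% | 95 | .27 |
| .10 | 417 | 72% | 117 | .75 |
| .15 | 442 | 68% | 142 | .98 |

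**The case against.** The strongest reply is that this is a gap in description rather than a demonstrated flaw. Consent is listed before participants hear their assigned components, so the burden of a condition cannot itself drive refusal. No text says the counselor sees the condition early. Eligibility has already been assessed by phone and is only confirmed at the visit. That is fair as far as it goes: staff knowledge is the only open route, and whether it is open in practice is not known. But the stated rule puts assignment before consent in an open-label trial, with consent taken by treatment-delivering staff, and states no safeguard. In that setting the plan has to state one.

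Second, re-issuing a condition does no harm in itself. This stands. In simulation (600 enrolled, blocks of 4, 20% background non-enrolment, 2,000 runs) the mean false difference was the same with and without re-issue: .005 and .005 for x = .05, r = .10; .028 and .027 for x = .15, r = .05. Re-issue matters only because it removes the signal in the arm sizes.

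Third, Appendix 1 is a request for health-system data, not the trial's allocation record; the Appendix 2 chart cannot be seen; and the Data and Safety Monitoring Plan has the principal investigators review numbers of and reasons for exclusions from enrolment. These soften the reporting point, but none of the available text promises a split by assigned condition.

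Fourth, every input to the size of the bias is assumed, and a log would detect a 5% one-arm loss with power of only .27. Both are true. The log guards against the larger losses, which are the ones that would matter. Concealment is the primary protection.

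**Conclusion.** The concern holds. As written, the Motivation and Cessation Studies assign the condition before eligibility is confirmed and consent signed, remove those who do not enrol, and state neither concealment from the consent-taker nor reporting of non-enrollers by condition. Limiting the point to these two studies is an inference from the reference to a treatment condition and from the Long-term Quitting design.

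The size and sign of any bias cannot be derived from the documents. Under the assumed one-arm losses, the consequence for the Cessation Study runs from negligible (type I error .053; power .76) to material (type I error .124; power .53). If concealment is already practised, stating it closes the first half of the point; the record by assigned condition is still needed. It should be fixed because the missing safeguard is basic and costs little.

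**What to change.** Either of two routes is acceptable.

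- **A. Assign later.** For people not yet assigned, generate the within-study condition (the four Motivation factors; AOCT or M-UC) at Visit 1, after written consent and baseline assessments. Stratify by gender and use balanced, blocked allocation. The Long-term Quitting Study already randomises through a real-time database.
- **B. Keep phone-screen assignment but lock it.** The database withholds the condition from candidates and consent-taking staff until consent and baseline are complete. Vacated conditions may still be re-issued. This suits a trial already recruiting, which the references to Spring 2018 suggest.

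Under either route, keep a record of everyone ever assigned (preserving any that already exists), report non-enrolled people by assigned condition in the CONSORT diagram, and define the analysis set in both studies as everyone consented and randomised. The text should also separate the study-level randomisation from the condition-level one.

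**Cost.** B needs protocol wording, an access lock and a log. A also moves the randomisation step: visit length is not known in advance, and staff must bring materials for every condition, although counselors are already trained in all counseling types. If A is adopted mid-trial there are two allocation periods, so the date of change must be recorded, and only later entrants are protected. Sample sizes and power do not change (.81 for 20% vs 30% at 300 per arm; .82 for 60% vs 72% at 256 per level).
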